9.2.1 Hospitalization as an SAE

Hospitalization is defined as any in-patient overnight stay in a hospital. A hospitalization in and of itself does not constitute an SAE. The condition which caused the hospitalization must be evaluated and determined to be an AE. Although an AE which results in hospitalization is an SAE, patients are hospitalized for a variety of reasons which may not be associated with or considered an SAE (eg, convenience, logistics, preference, etc). Therefore, each case of hospitalization must be evaluated separately.

For example, the following would not be considered SAEs:

- Hospitalization for a preexisting condition which did not worsen (eg, cataract surgery)
- Hospitalization solely for a procedure or treatment that was not performed to treat an AE
- Hospitalization for a condition that does not normally require treatment, but electively done (eg, cosmetic surgery)
- Hospitalization strictly for convenience reasons or observations (eg, procedures only performed in a hospital because of the distance the subject lives from the hospital)

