9.2 Serious Adverse Events (SAEs)

An SAE is defined as any event that results in any of the following outcomes:

1. Death
2. A life-threatening adverse event;
3. Inpatient hospitalization or prolonging of an existing hospitalization (see [Section 9.2.1](#) for information on hospitalization as an SAE);

4. A persistent or significant incapacity or substantial disruption of the ability to conduct normal life functions; or
5. A congenital anomaly/birth defect.

Important medical events that may not result in death, be life-threatening, or require hospitalization may be considered serious when, based upon appropriate medical judgment, they may jeopardize the subject and may require medical or surgical intervention to prevent one of the outcomes listed above.

Any SAE must be reported by telephone or facsimile within 24 hours of discovery of the event. Investigators should not wait to receive additional information to fully document the event before notifying the Sponsor of an SAE at:

Sites in North America must report to:

Safety Data [contact]

Safety [contact]

Email address (in case of fax failure): [contact]

Sites outside North America must report to the country specific toll-free fax numbers identified below:

Australia: [REDACTED]
Belgium: [REDACTED]
Brazil: [REDACTED]
France: [REDACTED]
Germany: [REDACTED]
Israel: [REDACTED]
Italy: [REDACTED]
Netherlands: [REDACTED]
Spain: [REDACTED]
Sweden: [REDACTED]
United Kingdom: [REDACTED]

Email Address (in case of fax failure): [REDACTED]

The telephone report should be followed by full written summary detailing relevant aspects of the SAE in question using the provided SAE report form. Where applicable, information from relevant hospital case records and autopsy reports should be obtained. The SAE should also be recorded on the AE page of the patient's CRF.

An SAE that occurs after completion of the study but, in the opinion of the Investigator, is related to the study medication, should be reported as described for an SAE. If an AE does not meet the regulatory definition of "serious" but is considered by the Investigator to be

related to the study medication and of such clinical concern as to influence the overall assessment of safety, it must be reported as defined for an SAE.

All patients (including discontinued patients) with a SAE must be followed until the event resolves or reaches a new Baseline, but for a minimum of 30 days after the last dose of study drug.

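### Section 9.2.1 gives two answers for an overnight stay to observe an AE: its general rule makes it an SAE, while its fourth example, read literally, does not

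*Protocol*

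**What the plan says.** Section 9.2 lists the outcomes that make an event serious. The third is "Inpatient hospitalization or prolonging of an existing hospitalization", with a cross-reference to Section 9.2.1 for how to apply it.

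Section 9.2.1 then does four things:

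- It defines the term: "Hospitalization is defined as any in-patient overnight stay in a hospital".
- It sets a test based on cause. A stay is not serious in itself: "The condition which caused the hospitalization must be evaluated and determined to be an AE".
- It states the general rule, "Although an AE which results in hospitalization is an SAE". The same sentence adds that patients may also be admitted for reasons such as convenience, logistics or preference, and the section concludes that "each case of hospitalization must be evaluated separately".
- It gives a list introduced by "For example, the following would not be considered SAEs". The second example exempts stays for a procedure or treatment, but only where the purpose was not to treat an AE. The fourth reads "Hospitalization strictly for convenience reasons or observations", and its one illustration is "procedures only performed in a hospital because of the distance the subject lives from the hospital".

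**The concern.** The definition and the general rule ask whether an AE led to an overnight stay. They do not ask whether the patient was treated or only watched. The fourth example classifies by purpose and names observation as a purpose that takes the stay out of the SAE category. It sets no condition on what prompted the observation. Because the second example does carry an AE condition, a careful site could take its absence from the fourth as deliberate.

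Safety and tolerability are the primary endpoint (Section 10.3.1). SAE incidence is a named safety endpoint (Section 10.3.2) and is summarized and listed (Sections 10.4.2 and 10.4.2.1). Seriousness also triggers the 24-hour report in Section 9.2 and is a precondition for the expedited reporting in Section 9.3. If sites resolve the conflict differently, SAE counts will vary with the reading and not only with what happened to patients. Some reports due within 24 hours will not be sent.

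**Working it through.** There is no stated figure to reproduce and no formula in the plan to test. The check sets the rules side by side and applies them to each kind of overnight stay.

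**Rules**

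- Rule A, from the definition and general rule in Section 9.2.1 and the third criterion in Section 9.2: overnight stay caused by an AE means SAE.
- Rule B, the fourth example read literally: stay strictly for convenience or observation means not an SAE.
- Rule B′, the fourth example read in context: the same, but only for stays not caused by an AE.

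**Cases**

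1. AE, overnight stay for treatment. A: SAE. B and B′ do not apply. Result: SAE.
2. No AE, overnight stay because the patient lives far from the hospital. A: not an SAE. B and B′: not an SAE. Consistent.
3. No AE, overnight stay for observation. A: not an SAE. B and B′: not an SAE. Consistent.
4. AE, overnight stay for observation only. A: SAE. B: not an SAE. B′ does not apply, so A stands: SAE.

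The conflict is confined to case 4, and there only between A and B. Two of the three readings keep the event in the SAE count; the literal one removes it. Section 9.2 does not settle the matter, because its third criterion refers the investigator to Section 9.2.1.

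**Other routes to an SAE report for case 4 under Rule B**

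- The remaining listed outcomes in Section 9.2 (death, threat to life, incapacity, birth defect) apply only if the event meets them independently.
- The important-medical-event paragraph is a matter of judgment: such events may be considered serious.
- A non-serious AE must still be reported as an SAE if the investigator considers it related to study drug and also of enough clinical concern to affect the overall safety assessment. Both conditions are needed.

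An overnight stay to observe an AE judged unrelated, or judged related but of limited concern, can pass all three.

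**Size**

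Let H be the number of AE-driven overnight stays, o the share for observation only, r the share of those classified by the literal reading, and b the share of those caught by another route. Then

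missed SAEs = H × o × r × (1 − b).

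The documents give none of H, o, r or b. The direction is known, since the product cannot be negative and each such error lowers the count. The amount is not.

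**The case against.** The strongest reply is that the section is clear when read in order. The causal test and the general rule come first. The list follows a sentence about stays for convenience, logistics and preference, and it is offered as illustration. The word *strictly*, the pairing of observation with convenience, and the travel-distance illustration all point to stays that no AE caused. Sites are also told to judge each case separately, so no example should be applied mechanically. On this view a patient kept overnight because of an AE is in hospital because of an AE, and the event is serious.

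Much of this stands. The contextual reading is the more likely intention. But the wording does not secure it. Observation is joined to convenience by *or*, is not among the non-SAE reasons named in the preceding sentence, and has no illustration of its own, since the distance illustration concerns convenience. Judging each case separately still means judging by the criteria given, and one of these conflicts with the rule.

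It is also fair that the event is not lost. It remains a recorded AE in the TEAE summaries and listings, and the quarterly DSMB review in Section 10.4.5 covers interim safety data generally. What is at risk is its classification as serious and what follows from that.

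**Conclusion.** The point holds as an internal inconsistency in a reporting definition. For an overnight stay to observe an AE, Section 9.2.1 read literally gives opposite answers. Sites may therefore differ on the same event, and any error from the literal reading lowers the SAE count and skips the 24-hour report. This rests on at least some sites applying the fourth example as written, and on the other clauses in Section 9.2 catching only part of what is missed.

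Three stronger inferences are tempting, and the documents do not support them:

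- *Admissions to observe an AE do drop out of the SAE count.* This follows only from the literal reading. The context favours the other one, so this is a risk and not a certainty.
- *The undercount is some percentage of hospitalization-based SAEs.* No rate of observation stays is given. Equating the undercount with an assumed share of such stays would also require every such stay to be classified literally and no other clause to catch any of them.
- *Phase 2 experience shows the problem.* The SAE described in Section 3.2.2 of the Amendment 1 text was assessed as possibly related, the patient was admitted for worsening nausea and vomiting and is not described as admitted for observation only, and the event was counted as an SAE. It does not illustrate the failure.

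The correction is small but worth making in a study whose primary endpoint is safety.

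**What to change.** Give the fourth example in Section 9.2.1 the kind of limit that the second already has, for instance: *hospitalization strictly for convenience, or for observation not prompted by an AE*. The travel-distance illustration can stay. This applies the section's own general rule and leaves dosing, visits and patient care unchanged.

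The cost is one clause, with the approval that Section 11.3 requires for any amendment. The SAE count may rise slightly, because short stays to observe an AE would then be classed as serious at every site.

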9.3 Suspected Unexpected Serious Adverse Reactions (SUSARs)

The FDA and/or other applicable Regulatory Authorities and all participating Investigators will be notified by a written Investigational New Drug Application (IND) safety report and/or other applicable regulatory report (eg, SUSAR) of any suspected adverse reaction that is both serious and unexpected, no later than 15 calendar days from the “date learned” of the event. In addition, all applicable regulatory bodies will be notified within 7 calendar days of any unexpected fatal or life-threatening suspected adverse reaction.

An adverse reaction is defined as any untoward and unintended response to an investigational medicinal product (IMP) related to any dose administered. This definition also covers medication errors and uses outside what is foreseen in the protocol, including misuse and abuse of the product. The definition also implies a reasonable possibility of a causal relationship between the event and the IMP.

An unexpected adverse reaction is any adverse drug event, which is not listed in the current Investigator's Brochure or is not listed at the specificity or severity that has been observed. For example, (A) a single occurrence of an event that is uncommon and known to be strongly associated with drug exposure (eg, angioedema, hepatic injury, Stevens-Johnson Syndrome); (B) 1 or more occurrences of an event that is not commonly associated with drug exposure, but is otherwise uncommon in the population exposed to the drug (eg, tendon rupture); (C) an aggregate analysis of specific events observed in a clinical trial (such as known consequences of the underlying disease or condition under investigation or other events that commonly occur in the study population independent of drug therapy) that indicates those events occur more frequently in the drug treatment group than in a concurrent or historical control group.

An untoward and unintended response to a non-IMP is by definition not a SUSAR.

9.4 Precautions

9.4.1 Pregnancy

Any patient (or patient's partner) who becomes pregnant during the study should be followed through delivery or termination of the pregnancy. In addition, patients who become pregnant during the study must be discontinued from the study treatment immediately.

In pregnancies that progress to term, any congenital abnormalities/birth defects in the offspring of a patient who received study medication should be reported as an SAE. The outcome of the pregnancy and the presence or absence of a congenital abnormality will be documented by completion of a Pregnancy Questionnaire and a Pregnancy Outcome Form in accordance with GCP and ICH guidelines and the Sponsor's SOPs.

Female patients should also notify the Investigator if they become pregnant within 30 days after last dose of study medication. Male patients should notify the Investigator if a female partner becomes pregnant within 30 days after last dose of study medication. The Sponsor must be notified of all pregnancies reported to the Investigator (see [Section 9.2](#) for contact information).

10. Statistical Methodology

10.1 Determination of Sample Size

No formal sample size calculation was made. The number of patients expected to participate in this study was calculated from estimated enrollment rates from other carcinoid cancer trials employed in the LX1606 clinical program.

10.2 Analysis Populations

Per protocol: A Per Protocol population will consist of those patients that receive study treatment and have no major protocol violation that would interfere with the collection or interpretation of the efficacy data. The primary analyses of efficacy will be based on the safety population; the per-protocol population will be used in a supplemental manner.

Safety: The safety population consists of all patients receiving any fraction of a dose of study drug during this study.

10.3 Study Endpoints

10.3.1 Efficacy Endpoints

The primary efficacy endpoint is to evaluate the long-term safety and tolerability of orally administered telotristat etiprate.

Secondary efficacy endpoint is to evaluate changes in patients' QOL over multiple years of therapy.

10.3.2 Safety Endpoints

Safety endpoints are as follows:

- Incidence of TEAEs, suspected adverse reaction, AEs leading to discontinuation from the study, SAEs, and deaths
- Actual and change from Baseline in clinical laboratory results
- Actual and change from Baseline in vital signs results
- Actual and change from Baseline in physical examinations
- Actual and change from Baseline in ECG findings

10.4 Statistical Methods

Descriptive analysis methods will be used to summarize the data. Continuous variables will be summarized by the N, mean, standard deviation, median, minimum, and maximum values. Categorical variables will be summarized as counts and related percentages. Data tabulations will be categorized by the treatment received on Day 1 of this study and combined across all treated patients. All data will be listed.

Primary analyses of the data will be based on the Safety population which includes all patients treated with any fraction of study drug during this study. Supportive analyses of the efficacy data will be made on a Per Protocol population. This dataset will include the Safety

population, but limited to those patients that have at least one assessment post Day 1 and do not have any protocol violations that would interfere with collection or interpretation of the data. The Per Protocol analysis will be applied to the QOL measures, subjective global assessment, and plasma 5-HIAA values.

Data will be summarized per study visit as the actual (raw) outcomes and change from Baseline scores, where applicable. Day 1 of this study will serve as the Baseline assessment.

10.4.1 Efficacy Analyses

All efficacy and PD variables will be summarized descriptively and listed.

Statistical tests and estimates of within patient effects for these measures will be derived from application of a mixed linear model with repeated measures. The model will be generalized to handle missing data and specific to the measurement properties of the dependent variable. There is no plan to impute data for missing observations for any variable. Non-parametric methods will be used to supplement the tests and estimates from the mixed linear model.

Exploratory analyses of treatment group differences may be performed by use of propensity score models. The treatments groups will correspond to how patients were dosed on Day 1 of this study.

10.4.2 Safety Analyses

Statistical analysis of the safety data will involve examination of the descriptive statistics and individual patient listings for any effects of study treatment on clinical tolerability and safety. Reporting of these data will be based on the Safety population. Summaries will be prepared by treatment group (corresponding to the LX1606 dose given on Day 1), pooled across all patients, and as needed, by study visit. All safety data will be listed.

Treatment-emergent adverse event summaries will include the overall incidence (by system organ class and preferred term), events by maximum intensity, event by relationship to study treatment, events leading to discontinuation of study drug, and serious adverse events.

Vital signs, ECG, and laboratory parameters (hematology, chemistry, and urinalysis) will be summarized descriptively at each time point. Actual and change from Baseline data will be calculated and summarized. In addition, shift table analysis will be applied to the laboratory data and summarized.

10.4.2.1 Adverse Events

All AEs will be coded and listed by body system and preferred term based on the Medical Dictionary for Regulatory Activities (MedDRA). Summaries using descriptive statistics will be provided for treatment-emergent AEs, drug-related AEs and AEs by intensity. Treatment-

emergent AEs are those events not present at Baseline, but occurring after the start of study drug, or if existing at Baseline, increasing in intensity after initiation study drug. Summaries made by intensity will select the event with the highest intensity when multiple occurrences of the same event are reported for the same patient. In a similar manner, summaries prepared by drug relationship will select the event with the greatest degree of relationship when a study reports multiple occurrences of the same event. On-study deaths will be reported for deaths occurring during the active phase of the treatment period and 30 days after stopping study drug. Also, deaths occurring outside the 30-day window, but secondary to an AE reported within the 30-day post treatment period, will be reported as well.

Listings will be provided for deaths, SAEs, and discontinuations due to AEs. Additional summaries or listings of AEs may also be provided.

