11.4.5 Retention of Study Documents

According to 21 CFR Part 312.62 and ICH E6, study-related records must be retained for at least 2 years after the last approval of a marketing application in an ICH region and until there are no pending or contemplated marketing applications in an ICH region, or at least 2 years have elapsed since the formal discontinuation of clinical development of the investigational product. These documents should be retained for a longer period, however, if required by applicable regulatory requirements or by an agreement with the Sponsor.

The Investigator must not destroy any study-related records without receiving approval from the Sponsor. The Investigator must notify the Sponsor in the event of accidental loss or destruction of any study records. If the Investigator leaves the institution where the study was conducted, the Sponsor must be contacted to arrange alternative record storage options.

12. Administrative Structure of the Study

Lexicon Pharmaceuticals, Inc.
[name]
[name]

Protocol No. LX1606.302

The study will be monitored by Sponsor personnel or Sponsor representative. The following functions for this study will be performed by organizations designated by the Sponsor: data management and statistical analysis, including PD analysis and reporting.

21 January 2015

CONFIDENTIAL

Page 44 of 59

CONFIDENTIAL
FINAL 24 February 2016

Page 236

INTERIM CLINICAL STUDY REPORT
LX1606.1-302-CS

13. Appendix A – Schedule of Events

Procedure	Extension Period								2-Week Follow-up ⁴
	Baseline Day 1 ¹	Week 12	Week 24	Week 36	Week 48	Week 60	Week 72	Week 84 / EOS	
Tolerance (days)	NA	± 5	± 5	± 5	± 5	± 5	± 5	± 5	± 5
Inclusion/Exclusion criteria	X								
Medical history	X								
Physical examination incl. weight	X	X ³	X ³	X ³	X	X ³	X ³	X	X ⁵
Urine pregnancy test ²	X	X	X	X	X	X	X	X	X
Serum pregnancy test ²									
Hematology, Blood chemistry	X	X	X	X	X	X	X	X	X ⁵
Urinalysis	X				X			X	X ⁵
Chromogranin A	X				X			X	
Vital signs	X	X	X	X	X	X	X	X	X
ECG	X				X			X	X ⁵
Subjective Global Assessment	X	X	X	X	X	X	X	X	X
EORTC QLQ-C30 & GI.NET21	X		X		X		X	X	
Sleep and Depression Assessment	X	X	X	X	X	X	X	X	X
Plasma 5-HIAA	X	X	X	X	X	X	X	X	X
Dispensation of LX1606	X	X	X	X	X	X	X		
Concomitant medications	X	X	X	X	X	X	X	X	X
Adverse events	X	X	X	X	X	X	X	X	X

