¹Eligibility will be determined at last visit of the original protocol; Day 1 will replace the next scheduled visit in the original protocol schedule. Visits should coincide with LAR injections for those patients receiving SSA therapy. ²Females of child-bearing potential only. ³Brief physical examination only (symptom-oriented, including weight). ⁴Visit to be performed for subjects who withdraw early and will not return for a 2-week follow-up visit; in all other cases the EOS visit should be performed followed by the follow-up visit 2 weeks postdose. ⁵To be performed only if evaluation at Week 48/84/EOS is abnormal.

14. Appendix B – Amount of Blood to be Collected from Each Patient

Assessment		Sample volume (mL)	Number of samples*	Estimated total volume (mL)
Safety	Hematology	2	9	18
	Blood chemistry	6	9	54
Other	CgA	2	3	6
Pharmacodynamic	Plasma 5-HIAA	4	9	36
Total				114
*Maximum number of samples is indicated				

During the past week:

	Not at All	A Little	Quite a Bit	Very Much
17. Have you had diarrhea?	1	2	3	4
18. Were you tired?	1	2	3	4
19. Did pain interfere with your daily activities?	1	2	3	4
20. Have you had difficulty in concentrating on things, like reading a newspaper or watching television?	1	2	3	4
21. Did you feel tense?	1	2	3	4
22. Did you worry?	1	2	3	4
23. Did you feel irritable?	1	2	3	4
24. Did you feel depressed?	1	2	3	4
25. Have you had difficulty remembering things?	1	2	3	4
26. Has your physical condition or medical treatment interfered with your family life?	1	2	3	4
27. Has your physical condition or medical treatment interfered with your social activities?	1	2	3	4
28. Has your physical condition or medical treatment caused you financial difficulties?	1	2	3	4

For the following questions please circle the number between 1 and 7 that best applies to you

29. How would you rate your overall health during the past week?

1 2 3 4 5 6 7

Very poor

Excellent

30. How would you rate your overall quality of life during the past week?

1 2 3 4 5 6 7

Very poor

Excellent

© Copyright 1995 EORTC Quality of Life Group. All rights reserved. Version 3.0

16. Appendix D – EORTC QLQ - GI.NET21

ENGLISH

EORTC QLQ – GI.NET21

Patients sometimes report that they have the following symptoms or problems. Please indicate the extent to which you have experienced these symptoms or problems during the past week. Please answer by circling the number that best applies to you.

During the past week:		Not at all	A little	Quite a bit	Very much	

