6.3 Criteria for Stopping Treatment/Study Withdrawal

A patient may also be discontinued from the study for the following medical or administrative reasons:

- Withdrawal of consent by the patient or legal guardian
- Noncompliance, including refusal of the study medication and/or failure to adhere to the study requirements as in the study protocol
- Investigator decides that, in the interest of the patient, it is not medically acceptable to continue participation in the study
- The Sponsor terminates the study ([Section 6.4](#))
- Pregnancy ([Section 9.4.1](#))

Note: If a patient voluntarily withdraws or is discontinued from study treatment before completing the entire duration of the Treatment Period, they should be encouraged to continue clinic visits according to the study schedule.

Patients who discontinue study treatment, and who are not willing to continue clinic visits (eg, withdrawal of consent) should be encouraged to complete End-of-Study (EOS) assessments as identified in [Appendix A](#) – Schedule of Events and agree to report any SAEs (Section 9.2) that occur within 30 days following the last dose of telotristat etiprate.

The date the patient discontinues study treatment, the primary reason for study treatment discontinuation, study termination, and/or termination of participation (eg, withdrawal of consent), will be captured within the Case Report Form (CRF).

When patients withdraw consent from study participation, it must be recorded on the CRF whether the withdrawal of consent applies to specific aspects of the study such as discontinuation of study treatment, participation in study visits, contact by study personnel, or

access to information about potential SAEs. If specific consent has not been withdrawn, study personnel should contact the patient (or a previously approved designee such as a caregiver, partner, or family member) at the scheduled Follow-up visit to inquire about health status.

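### Deaths are counted to 30 days after the last dose, but in patients who complete follow-up a new fatal event judged unrelated has no scheduled contact or explicit reporting duty after the 2-week visit

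*Protocol*

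**What the plan says.** **Analysis window.** Section 10.4.2.1 sets the rule for the death count, whatever the cause: "On-study deaths will be reported for deaths occurring during the active phase of the treatment period and 30 days after stopping study drug". It also reports "deaths occurring outside the 30-day window, but secondary to an AE reported within the 30-day post treatment period". Section 10.3.2 names SAEs and deaths among the safety endpoints.

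**Scheduled contact.** In Appendix A, the last column in which adverse events are recorded is the 2-week follow-up. Footnote 4 gives a special rule for early withdrawals and then says that "in all other cases the EOS visit should be performed followed by the follow-up visit 2 weeks postdose". The tolerance row allows ± 5 days. No day-30 contact is listed. The Amendment 2 rationale gives total participation as up to 86 weeks, which is 84 weeks of treatment plus 2 of follow-up.

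**Reporting duties.**
- Section 9.2 requires any SAE to be reported within 24 hours of discovery and gives no end date.
- Section 9.2 separately says what is to be reported later: "An SAE that occurs after completion of the study but, in the opinion of the Investigator, is related to the study medication".
- Section 9.2 has patients with an SAE followed for at least 30 days after the last dose. Section 9.1 has known AEs followed for 30 days, or until they resolve or stabilise.
- Section 6.3 (Amendment 1 text) asks patients who stop treatment and decline further visits to report any SAEs "that occur within 30 days following the last dose of telotristat etiprate".

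**The concern.** The deaths table presupposes that every patient is observed to day 30, since both sentences in Section 10.4.2.1 rely on information up to that day. The collection rules do not clearly provide it. A patient who completes treatment and attends the 2-week visit has then completed the study. If that patient dies on day 20 of a new event that the investigator calls unrelated, the death belongs in the table, but nothing schedules a contact that would find it, and the only sentence written for events after completion does not ask for it.

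Two consequences follow. Whether such a death is counted can depend on a causality opinion given without blinding, although the definition of the count has no causality element. Ascertainment can also differ by disposition: the patient who stops early and refuses visits has an express 30-day request for any SAE, and the completer does not. Long-term safety is the primary objective, so the completeness of this count matters. An analysis plan cannot repair it later, because events that were not collected cannot be analysed.

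**Working it through.** The protocol states no figure to reproduce here. The check sets the windows side by side and then sizes the interval.

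**1. Inputs**
- End of the death window: day 30 after the last dose (Section 10.4.2.1).
- Last scheduled contact: day 14 ± 5, so day 9 to day 19 (Appendix A and footnote 4).
- Patients: up to 100 (Section 6, Amendment 1 text).
- Annual mortality *m*: not given in the protocol. I assume 5%, 10% and 20%, for illustration only.

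**2. Days without a scheduled contact** = 30 − day of last visit
- Visit on day 14: 30 − 14 = 16 days (16/30 = 53% of the window).
- Visit on day 19: 30 − 19 = 11 days (37%).
- Visit on day 9: 30 − 9 = 21 days (70%).

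**3. Expected deaths in that interval**, if all 100 patients were exposed to it: 100 × [1 − (1 − *m*)^(days/365)]

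| Interval | *m* = 5% | *m* = 10% | *m* = 20% |
|---|---|---|---|
| 11 days | 0.15 | 0.32 | 0.67 |
| 16 days | 0.22 | 0.46 | 0.97 |
| 21 days | 0.29 | 0.60 | 1.28 |
| Full 30 days | 0.42 | 0.86 | 1.82 |

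These are deaths expected to occur in the interval, so they are upper bounds on deaths missed.

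**4. Which events have a route to the database between the last visit and day 30?**
- *SAE or unresolved AE already known at the visit:* yes, regardless of causality, through the follow-up rules in Sections 9.1 and 9.2.
- *New SAE in an early discontinuer who declines visits:* yes, any cause, to 30 days (Section 6.3, Amendment 1 text).
- *Early discontinuer who stays on the visit schedule:* may still be seen at later clinic visits, which Section 6.3 (same text) encourages.
- *New SAE in a completer, judged related:* yes, under the post-completion sentence in Section 9.2.
- *New SAE in a completer, judged unrelated:* only the general 24-hour rule could apply. It works on discovery, and no contact is scheduled at which discovery would occur.

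Only the last category lacks a clear route.

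**5. Comparison within the protocol.** For pregnancy, Section 9.4.1 sets a 30-day notification period after the last dose that applies to all patients. The sections shown set no equivalent period for SAEs and deaths.

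**The case against.** The strongest reply is that the general rule in Section 9.2, under which any SAE is reportable within 24 hours of discovery, has no end date. The sentence about related SAEs after completion can then be read as an open-ended addition to that rule rather than a limit on it. Section 10.4.2.1 itself mentions AEs reported in the 30 days after treatment, which suggests that the authors expected reporting to day 30. Section 9.1 refers to a reporting period without defining it in the text shown. On this view the protocol is unclear rather than deficient.

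Part of this stands. A reader might infer that after 2 weeks only drug-related SAEs are reportable, that every unrelated death in the 16 days is missed, or that the count will certainly be too low. The documents do not support any of these. Known SAEs and AEs are followed to 30 days whatever their attribution (AEs that resolve or stabilise may be released sooner), some early discontinuers have an any-SAE request, and the general rule is not expressly closed. The 16 days are days without a scheduled contact, not days without any reporting.

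The reply does not remove the residual gap. If the general rule ran without limit, a separate sentence for related SAEs after completion would add nothing, so a site could reasonably take it as the operative rule. An unlimited duty would still depend on someone learning of the event.

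**Conclusion.** The point holds in a narrow form. For patients who complete follow-up, a new-onset fatal event judged unrelated, falling between the 2-week visit and day 30, has no scheduled contact and no explicit reporting duty, yet it belongs in the Section 10.4.2.1 count. The interval is about 16 days (11 to 21). The count may therefore be incomplete and partly dependent on an open-label causality opinion.

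The likely number is small: at most about 0.2 to 1.0 deaths per 100 patients for a day-14 visit, and 0.15 to 1.28 across the visit tolerance, under assumed mortality of 5% to 20% a year. One death can still matter in a listing of this size. The change should be made, but the gap does not put the study's validity in doubt.

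The conclusion assumes that the current Section 6.3 matches the Amendment 1 wording; the current text is not in the part at hand, and the Amendment 2 change list shows no change to it. It also assumes that no text outside the sections seen, including any opening paragraph of Section 9, already sets a 30-day all-cause reporting period. That should be checked before the change is drafted.

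**What to change.** Reconcile Sections 6.3, 9.2 and 10.4.2.1 and Appendix A around one collection period:
- In Section 9.2, require all SAEs and deaths through 30 days after the last dose to be reported for every patient, regardless of causality and of whether the patient completed or stopped early. Keep related-only reporting for events after day 30.
- In Appendix A, add a day-30 check of vital status and SAEs by a short telephone call or chart review.
- In Section 6.3, refer to the same period, so that completers and early discontinuers are treated alike.
- In Section 10.4.2.1, use the same 30-day window for post-treatment SAEs as for deaths.

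The cost is protocol wording and one brief contact per patient, with no added visit or procedure. The reported count of deaths and SAEs may rise slightly, and that rise would reflect more complete ascertainment.
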